1 PROTOCOL SUMMARY

1.1 Synopsis

Title: A Phase 1/2 Study of Delayed Heterologous SARS-CoV-2 Vaccine Dosing (Boost) after Receipt of EUA Vaccines.

Phase: Phase 1/2

Population: Approximately 1130 healthy individuals aged ≥ 18 years

Sites: Approximately 10 clinical research sites.

Rationale:

The Severe Acute Respiratory Syndrome Coronavirus 2 (SARS-CoV-2), causative agent of the coronavirus disease of 2019 (COVID-19) pandemic, has infected over 182 million people worldwide and resulted in over 3.9 million deaths, including $> 605,000$ in the United States (July 02, 2021, WHO; (www.who.int). Multiple Phase 3 efficacy trials of SARS-CoV-2 vaccine constructs are underway or in long-term follow-up in the U.S, and these studies have supported 3 Emergency Use Authorizations (EUAs) for COVID vaccines. The emergence of variant strains has raised concerns about the breadth of immunity and protection achieved by the current vaccines. WHO SAGE and CDC ACIP have identified the safety and immunogenicity of mixed schedules as a critical and immediate research priority to inform policy on the use of mixed schedules.

Knowledge of the safety, tolerability, and immunogenicity of a boost vaccine using a heterologous platform with the homologous or variant spike lineage administered after an EUA primary dosing is a critical piece of information needed to inform public health decisions. The heterologous boost strategy will also provide an opportunity to thoroughly evaluate innate, cellular, and humoral immune responses elicited from the multiple prime boost combinations using very similar immunogens, utilizing mRNA, adenovirus- vectored, and protein-based platforms. As new vaccines are manufactured to emerging variants, these foundational data will be key to the evaluation of future variant and heterologous prime-boost strategies. This phase 1/2 clinical trial will evaluate the safety and immunogenicity of different heterologous delayed doses (boosts) in those who received an EUA vaccine (either prior to participation in this trial, or as part of this trial).

Objectives:

Primary:

1. To evaluate the safety and reactogenicity of delayed heterologous or homologous vaccine doses after EUA dosed vaccines:
 - Local and systemic solicited adverse events for 7 days following the delayed boost dose.

- Adverse Events from Dose 1 to 28 days following each vaccination and delayed boost dose.
 - MAAEs, SAEs, NOCMCs, and AESIs from Dose 1 to end of planned study participation .
2. To evaluate humoral immunogenicity of heterologous booster vaccines following EUA dosing.

Exploratory:

1. To assess, in at least a subset of samples, the B cell immune response following EUA vaccination and delayed boost;
2. To assess, in at least a subset of samples, the SARS-CoV-2 protein-specific T cell responses following EUA vaccination and delayed boost;
3. To evaluate breakthrough symptomatic SARS-CoV-2 infection and sequence strains to assess for variant spike lineage.
4. To assess, in at least a subset of samples, mucosal (salivary and nasal) SARS-CoV-2 spike protein-specific IgG and IgA responses and assess correlation with serologic responses.

Study Design:

This Phase 1/2 study will evaluate the safety, tolerability, immunogenicity of different SARS-CoV-2 vaccine delayed boost at ≥ 12 weeks. This study will be composed of two different cohorts:

1. A cohort of persons previously vaccinated with an EUA vaccine who will be boosted with a homologous or heterologous vaccine strain on a homologous or a heterologous platform (

Group	Sample Size*	EUA Dosing Scheme	Interval(weeks)	Delayed Booster Vaccination	Strategy Tested
1E	50	Previously dosed Janssen – Ad26.COVID-2-S	≥ 12	Moderna-mRNA-1273	Same Strain Heterologous platform
2E	50	Previously dosed Moderna – mRNA-1273	≥ 12	Moderna-mRNA-1273	Control - Same Strain & platform
3E	50	Previously dosed Pfizer/BioNTech – BNT162b2	≥ 12	Moderna-mRNA-1273	Same Strain Similar platform
4E	50	Previously dosed Janssen – Ad26.COVID-2-S	≥ 12	Janssen – Ad26.COVID-2.S	Control - Same Strain & platform

Group	Sample Size*	EUA Dosing Scheme	Interval(weeks)	Delayed Booster Vaccination	Strategy Tested
5E	50	Previously dosed Moderna – mRNA-1273	≥12	Janssen – Ad26.COVS.2.S	Same Strain Heterologous platform
6E	50	Previously dosed Pfizer/BioNTech –BNT162b2	≥12	Janssen – Ad26.COVS.2.S	Same Strain Heterologous platform
7E	50	Previously dosed Janssen – Ad26.COVS.2.S	≥12	Pfizer/BioNTech –BNT162b2	Same Strain Heterologous platform
8E	50	Previously dosed Moderna – mRNA-1273	≥12	Pfizer/BioNTech-BNT162b2	Same Strain Similar platform
9E	50	Previously dosed Pfizer/BioNTech –BNT162b2	≥12	Pfizer/BioNTech –BNT162b2	Control - Same Strain & platform
10E	50	Previously dosed Janssen – Ad26.COVS.2.S	≥12	Moderna-mRNA-1273.211	Variant Strain Heterologous platform
11E	50	Previously dosed Pfizer/BioNTech –BNT162b2	≥12	Moderna-mRNA-1273.211	Variant Strain Similar platform
12E	50	Previously dosed Janssen – Ad26.COVS.2.S	≥12	Moderna-mRNA-1273 50 mcg	Same Strain Heterologous platform
13E	50	Previously dosed Moderna – mRNA-1273	≥12	Moderna-mRNA-1273 50 mcg	Control - Same Strain & platform
14E	50	Previously dosed Pfizer/BioNTech –BNT162b2	≥12	Moderna-mRNA-1273 50 mcg	Same Strain Similar platform
15E	60	Previously dosed +/- boosted Janssen – Ad26.COVS.2.S	≥12	NVX-CoV2373 5 mcg SARS-CoV-2 rS 50 mcg Matrix-M	Same Strain Heterologous platform
16E	60	Previously dosed Moderna – mRNA-1273	≥12	NVX-CoV2373 5 mcg SARS-CoV-2 rS 50 mcg Matrix-M	Same Strain Heterologous platform
17E	60	Previously dosed	≥12	NVX-CoV2373 5 mcg SARS-CoV-2 rS	Same Strain Heterologous platform

Group	Sample Size*	EUA Dosing Scheme	Interval(weeks)	Delayed Booster Vaccination	Strategy Tested
		Pfizer/BioNTech –BNT162b2		50 mcg Matrix-M	

2.); and
3. A cohort of persons who are prospectively vaccinated with EUA standard dosing and who will be available for rapid assessment of a heterologous boost at some point in the future (Table 2).

EUA-dosed Cohort: Cohort 1 will recruit persons who have previously received COVID-19 vaccine under EUA dosing guidelines, completing their regimen at least 12 weeks prior to enrollment. Eligible individuals will be stratified by age group (18-55 years or ≥ 56 years) in a 1:1 ratio (N = 25/group*). Subjects will be sequentially enrolled to receive one of the available delayed boost options (

[figure not shown]

Group	Sample Size*	EUA Dosing Scheme	Interval(weeks)	Delayed Booster Vaccination	Strategy Tested
1E	50	Previously dosed Janssen – Ad26.COVS2-S	≥ 12	Moderna- mRNA-1273	Same Strain Heterologous platform
2E	50	Previously dosed Moderna – mRNA-1273	≥ 12	Moderna- mRNA-1273	Control - Same Strain & platform
3E	50	Previously dosed Pfizer/BioNTech – BNT162b2	≥ 12	Moderna- mRNA-1273	Same Strain Similar platform
4E	50	Previously dosed Janssen – Ad26.COVS2-S	≥ 12	Janssen – Ad26.COVS2.S	Control - Same Strain & platform
5E	50	Previously dosed Moderna – mRNA-1273	≥ 12	Janssen – Ad26.COVS2.S	Same Strain Heterologous platform
6E	50	Previously dosed Pfizer/BioNTech – BNT162b2	≥ 12	Janssen – Ad26.COVS2.S	Same Strain Heterologous platform
7E	50	Previously dosed Janssen – Ad26.COVS2-S	≥ 12	Pfizer/BioNTech – BNT162b2	Same Strain Heterologous platform
8E	50	Previously dosed Moderna – mRNA-1273	≥ 12	Pfizer/BioNTech- BNT162b2	Same Strain Similar platform
9E	50	Previously dosed Pfizer/BioNTech – BNT162b2	≥ 12	Pfizer/BioNTech – BNT162b2	Control - Same Strain & platform

Group	Sample Size*	EUA Dosing Scheme	Interval(weeks)	Delayed Booster Vaccination	Strategy Tested
10E	50	Previously dosed Janssen – Ad26.COV2-S	≥12	Moderna- mRNA-1273.211	Variant Strain Heterologous platform
11E	50	Previously dosed Pfizer/BioNTech – BNT162b2	≥12	Moderna- mRNA-1273.211	Variant Strain Similar platform
12E	50	Previously dosed Janssen – Ad26.COV2-S	≥12	Moderna- mRNA-1273 50 mcg	Same Strain Heterologous platform
13E	50	Previously dosed Moderna – mRNA-1273	≥12	Moderna- mRNA-1273 50 mcg	Control - Same Strain & platform
14E	50	Previously dosed Pfizer/BioNTech – BNT162b2	≥12	Moderna- mRNA-1273 50 mcg	Same Strain Similar platform
15E	60	Previously dosed +/- boosted Janssen – Ad26.COV2-S	≥12	NVX-CoV2373 5 mcg SARS-CoV-2 rS 50 mcg Matrix-M	Same Strain Heterologous platform
16E	60	Previously dosed Moderna – mRNA-1273	≥12	NVX-CoV2373 5 mcg SARS-CoV-2 rS 50 mcg Matrix-M	Same Strain Heterologous platform
17E	60	Previously dosed Pfizer/BioNTech – BNT162b2	≥12	NVX-CoV2373 5 mcg SARS-CoV-2 rS 50 mcg Matrix-M	Same Strain Heterologous platform

). A total of approximately 50* per group will be recruited for each group (combination of EUA primary vaccination plus booster) in Cohort 1. *Note: Due to the surge in Omicron variant cases, vaccinated individuals may be prone to asymptomatic breakthrough infections. Stage 6 (Groups 15E-17E) sample size will be expanded to N = 60/group (approximately 1:1 age strata). This study is designed to be adaptive, and as more vaccines become available either under EUA (or anticipated to have an EUA in the next few months), or new variants of available EUA vaccines become available, the number of groups may be expanded. Participants will be assessed for safety and tolerability endpoints following administration of a delayed boost.

Table 1: EUA-dosed Cohort 1

Group	Sample Size*	EUA Dosing Scheme	Interval(weeks)	Delayed Booster Vaccination	Strategy Tested
1E	50	Previously dosed Janssen – Ad26.COV2-S	≥12	Moderna- mRNA-1273	 Same Strain Heterologous platform

Group	Sample Size*	EUA Dosing Scheme	Interval(weeks)	Delayed Booster Vaccination	Strategy Tested
2E	50	Previously dosed Moderna – mRNA-1273	≥12	Moderna- mRNA-1273	 Control - Same Strain & platform
3E	50	Previously dosed Pfizer/BioNTech – BNT162b2	≥12	Moderna- mRNA-1273	 Same Strain Similar platform
4E	50	Previously dosed Janssen – Ad26.COVID-2-S	≥12	Janssen – Ad26.COVID-2.S	 Control - Same Strain & platform
5E	50	Previously dosed Moderna – mRNA-1273	≥12	Janssen – Ad26.COVID-2.S	 Same Strain Heterologous platform
6E	50	Previously dosed Pfizer/BioNTech – BNT162b2	≥12	Janssen – Ad26.COVID-2.S	 Same Strain Heterologous platform
7E	50	Previously dosed Janssen – Ad26.COVID-2-S	≥12	Pfizer/BioNTech – BNT162b2	 Same Strain Heterologous platform
8E	50	Previously dosed Moderna – mRNA-1273	≥12	Pfizer/BioNTech- BNT162b2	 Same Strain Similar platform
9E	50	Previously dosed Pfizer/BioNTech – BNT162b2	≥12	Pfizer/BioNTech – BNT162b2	 Control - Same Strain & platform
10E	50	Previously dosed Janssen – Ad26.COVID-2-S	≥12	Moderna- mRNA-1273.211	 Variant Strain Heterologous platform
11E	50	Previously dosed Pfizer/BioNTech – BNT162b2	≥12	Moderna- mRNA-1273.211	 Variant Strain Similar platform
12E	50	Previously dosed Janssen – Ad26.COVID-2-S	≥12	Moderna- mRNA-1273 50 mcg	 Same Strain Heterologous platform
13E	50	Previously dosed Moderna – mRNA-1273	≥12	Moderna- mRNA-1273 50 mcg	 Control - Same Strain & platform
14E	50	Previously dosed Pfizer/BioNTech – BNT162b2	≥12	Moderna- mRNA-1273 50 mcg	 Same Strain Similar platform
15E	60	Previously dosed +/- boosted Janssen – Ad26.COVID-2-S	≥12	NVX-CoV2373 5 mcg SARS-CoV-2 rS 50 mcg Matrix-M	 Same Strain Heterologous platform
16E	60	Previously dosed Moderna – mRNA-1273	≥12	NVX-CoV2373 5 mcg SARS-CoV-2 rS	 Same Strain Heterologous platform

Group	Sample Size*	EUA Dosing Scheme	Interval(weeks)	Delayed Booster Vaccination	Strategy Tested
17E	60	Previously dosed Pfizer/BioNTech – BNT162b2	≥12	50 mcg Matrix-M NVX-CoV2373 5 mcg SARS-CoV-2 rS 50 mcg Matrix-M	 Same Strain Heterologous platform

*Sample cohort size, N = approximately 50, two age strata: 18-55 years (n ≈ 25), ≥ 56 years (n ≈ 25), and N= approximately 60, two age strata (N~ 30) for Groups 15E-17E.

Prospective Cohort: Cohort 2 will recruit persons who are naïve to COVID-19 vaccine and infection (by history). These individuals will be given a vaccine as part of the study that matches the vaccine/dose available under an EUA. Cohorts from this pool will then be available to be boosted with a novel homologous or heterologous variant lineage spike proteins or heterologous platform delayed boost as part of an adaptive design meant to respond quickly to circulating SARS-CoV-2 variants. As booster vaccines have been approved for individuals at an interval of 6 months from the primary series, under EUA, all Cohort 2 volunteers will be offered a booster of mRNA-1273 at the approved 50 mcg dose. Due to the surge of the Omicron variant and breakthrough infections, volunteers who contract symptomatic or asymptomatic COVID-19 between completion of their EUA primary series and the scheduled booster dose will be allowed to continue in the study. The interval between the COVID-19 infection and booster dosing should be a minimum of 28 days. This pool of participants will then be followed to assess the immunogenicity of a 4th dose of bivalent vaccine. The Moderna mRNA-1273.222 vaccine that contains 25-mcg of the prototype strain and 25-mcg of the Omicron BA.4/BA.5 variant (total 50-mcg) will be administered as a second booster 4 to 12 months after administration of the first booster vaccine.

Prioritization of Cohort 1 versus Cohort 2 enrollment will be determined by availability of EUA-dosed vaccines, status of distribution, and current epidemiology. Cohorts 1 and 2 may enroll simultaneously.

Table 2: Prospective Cohort 2

Group	Sam- ple Size*	First Vaccina- tion**	Inter- val	Second Vaccina- tion**	Inter- val	Delayed Booster Vaccina- tion 1	Interval	Booster Vaccination 2
1	250	Moderna- 100 mcg mRNA- 1273	28 days	Moderna- 100 mcg mRNA- 1273	~6 months	Moderna - 50 mcg mRNA- 1273	4-12 months	Moderna - 50 mcg mRNA- 1273.222

*Aged \geq 18 years

** As part of an adaptive design, products newly awarded EUA can be added as programmatically needed.

Duration of Study: Approximately 4 years

Duration of participation per subject: Up to 2 years (approximately ~6 months after second booster inoculation)

Criteria for Inclusion/Exclusion:

Inclusion Criteria:

Participants must meet all of the following criteria to be eligible to participate in this study:

1. Individuals \geq 18 years of age at the time of consent.
2. Received and completed primary mRNA COVID-19 vaccine under EUA dosing guidelines and one or two doses of Ad26.COVS.2 at least 12 weeks prior to enrollment (Cohort 1 only).
3. Willing and able to comply with all scheduled visits, vaccination plan, laboratory tests and other study procedures.
4. Determined by medical history, targeted physical examination and clinical judgement of the investigator to be in good health.

Note: Healthy volunteers with pre-existing stable disease, defined as disease not requiring significant change in therapy or hospitalization for worsening disease during the 6 weeks before enrollment, can be included.

5. Female participants of childbearing potential may be enrolled in the study, if all of the following apply:
 - Practiced adequate contraception for 28 days prior to the first dose of vaccine (Day 1),
 - Has agreed to continue adequate contraception through 3 months following the booster dose,
 - Has a negative pregnancy test at screening and on the day of the first study vaccine dose (Day 1),

- Is not currently breastfeeding.

Exclusion Criteria:

Participants meeting any of the following criteria will be excluded from the study:

1. Known history of SARS-CoV-2 infection (for Cohort 1 and the primary series of Cohort 2).
2. Prior administration of an investigational coronavirus (SARS-CoV, MERS-CoV) vaccine or SARS-CoV-2 monoclonal antibody in the preceding 90 days or current/planned simultaneous participation in another interventional study.
3. Receipt of SARS CoV-2 vaccine prior to study entry (Cohort 2 only).
4. A history of anaphylaxis, urticaria, or other significant adverse reaction requiring medical intervention after receipt of a vaccine or nanolipid particles.
5. Receipt of any investigational study product within 28 days prior to enrollment.
6. Received or plans to receive a vaccine within 28 days prior to the first dose (Day 1) or plans to receive a non-study vaccine within 28 days prior to or after any dose of study vaccine (with exception for seasonal influenza vaccine within 14 days of study vaccine).
7. Bleeding disorder diagnosed by a doctor (e.g., factor deficiency, coagulopathy, or platelet disorder requiring special precautions) or significant bruising or bleeding difficulties with intramuscular injections or blood draws, or previously experienced thrombosis with thrombocytopenia (TTS) or heparin-induced thrombocytopenia.
8. Current or previous diagnosis of immunocompromising condition, immune-mediated disease, or other immunosuppressive condition.
9. Received systemic immunosuppressants or immune-modifying drugs for >14 days in total within 6 months prior to Screening (for corticosteroids ≥ 20 mg/day of prednisone equivalent). Topical tacrolimus is allowed if not used within 14 days prior to Day 1.
10. Received immunoglobulin, blood-derived products, within 90 days prior to first study vaccination.
11. An immediate family member or household member of this study's personnel.
12. Is acutely ill or febrile 72 hours prior to or at vaccine dosing (fever defined as $\geq 38.0^{\circ}\text{C}/100.4^{\circ}\text{F}$). Participants meeting this criterion may be rescheduled within the relevant window periods. Afebrile participants with minor illnesses can be enrolled at the discretion of the investigator.

Safety

- The study will use halting rules for booster vaccination in the study overall and not EUA dosed vaccinations to individual subjects. See [Section 7.1](#) for details.
- This study will use a Safety Monitoring Committee (SMC) for objective oversight of the study. SMC reviews are required for study halting.

1.2 Schedule of Activities (SOA)

Table 3: SOA for EUA-dosed Cohort 1

Study Day	D-28 to D-1	1	8 ^b	15	29	91	181	273	366	Illness/ Unscheduled Visit	Early Termination Visit
Visit Number	00 ^a	1	2	3	4	5	6	7	8		
Window (+/-)		0	1	2	2	7	14	28	28		
Informed Consent ^a	X										
Eligibility Criteria	X	X									
Medical History	X	X									
Vaccination ^c		X									
Concomitant Meds		X	X	X	X						
Interim History		X	X	X	X	X	X	X	X	X	X
Physical Exam - Targeted	X	X		X	X	X	X	X	X	X	X
Vital Signs ^d	X	X		X	X					X	X
Height/Weight (BMI) ^a	X										
Urine β-HCG ^e		X									
Memory Aid, Solicited AEs		X	X	X ^f							
Unsolicited AEs		X	X	X	X						
SAEs, Protocol specified AESIs, MAAEs, and NOCMCs			X	X	X	X	X	X	X	X	X
Nasal or NP swab for PCR & Sequencing										X ^g	
Immunoassays											
Serum- Humoral Assays		32		32	32	32	32	32	32		32
PBMC Cellular Assays & plasma		64		64			64		64		64
Daily Volume (mL)		96		96	32	32	96	32	96		96
Cumulative Volume (mL)		96		192	224	256	352	384	480		

^a Optional screening visit – informed consent and height/weight only performed at screening or Day 1

^b Telephone visit

^c Delayed booster dose based upon assignment to Groups 1E-3E (and/or future groups added as adaptive design)

^d Vital signs before and after booster vaccination. Otherwise, only as clinically indicated

^e For women of childbearing potential, a negative urine pregnancy on Day 1 will be performed with negative results confirmed before dosing

^f Review 7-day Memory Aid data.

^g Collect nasal or NP swab for PCR (x2). Sequencing will be performed on all Illness visit-confirmed SARS-CoV-2 specimens.

Table 4: SOA for Prospective Cohort 2 (prior to 2nd booster dose):

Study Day	D-28 to D-1	1	8 ^b	29	36 ^b	43	Delayed Boost to occur ≥ 181 days (window +/- 30 days) from Dose 2	1B	8B ^b	15B	29B	91B	181B	366B	Illness/Unsch Visit	Early Term Visit
Visit Number	00 ^a	1	2	3	4	5		6	7	8	9	10	11	12		
Window (+/-)		0	1	2	3	3		0 ^d	1	2	2	7	14	28		
Informed Consent ^a	X															
Eligibility Criteria	X	X		X				X								
Medical History	X															
Vaccination		X ^c		X ^c				X ^d								
Concomitant Meds	X	X	X	X	X	X		X	X	X	X					
Interim History		X	X	X	X	X		X	X	X	X	X	X	X	X	X
Physical Exam - Targeted	X	X		X		X		X			X	X	X	X	X	X
Vital Signs ^e	X	X		X				X			X	X			X	
Height/Weight (BMI) ^a	X															
Urine β-HCG ^f		X		X				X								
Memory Aid, Solicited AEs		X	X	X	X			X	X	X ^g						
Unsolicited AEs		X	X	X	X	X		X	X	X	X					
SAEs, Protocol specified AESIs, MAAEs, and NOCMCs			X	X	X	X		X	X	X	X	X	X	X	X	X
Nasal or NP swab for PCR & Sequencing															X ^h	
Immunoassays																
Serum- Humoral Assays		32		32		32		32		32	32	32	32	32		32
PBMC Cellular Assays & plasma		64*		64*		64*	64		64	64	64	64	64		64	
Daily Volume (mL)		96		96		96	96		96	32	96	96	96		96	
Cumulative Volume (mL)		96		192		192	384		480	512	608	704	800			

^a Optional screening visit – informed consent and height/weight only performed at screening or Day 1

^b Telephone visit

^c EUA-dosing with 28-day interval – new constructs may be added as EUA is awarded and vaccine available

^d Delayed booster dose will be the 50 mcg dose of Moderna mRNA-1273. It will be administered on study day 1B which is 181 days with a window of +28 days after the second vaccine dose. If no booster administered; safety visits will continue as per [Table 6](#). If Covid-19 infection is detected in the interval between the primary series and the estimated time of booster administration, volunteers may remain in the study (with a minimum 28 day interval between infection and boost)

^e Vital signs before and after vaccination. Otherwise, only as clinically indicated.

^f For women of childbearing potential, a negative urine pregnancy test on Days 1 and 1B (delayed boost) will be performed with negative results confirmed prior to each dosing

^g Review 7-day Memory Aid data for delayed booster dose.

^h Collect nasal or NP swabs (x 2) for PCR. Sequencing will be performed on all illness visit-confirmed SARS-CoV-2 specimens.

*Collection of PBMC for cellular assays is performed at the discretion of the site, based on the capacity for PBMC processing

Table 5: SOA for Prospective Cohort 2 (2nd booster dose)

Study Day		1C	8C ^b	15C	29C	91C	181C	Illness/Unsch Visit	Early Term Visit
Visit Number		13	14	15	16	17	18		
Window (+/-)		0	1	2	2	7	14		
Informed Consent		X							
Eligibility Criteria		X							
Vaccination		X ^a							
Concomitant Meds		X	X	X	X				
Interim History		X	X	X	X	X	X	X	X
Physical Exam - Targeted		X		X	X	X	X	X	X
Vital Signs ^c		X		X	X			X	
Saliva Mucosal Sample		X		X	X	X	X		X
Nasal Mucosal Sample		X		X	X	X	X		X
Urine β-HCG ^d		X							
Memory Aid, Solicited AEs	Boost to occur ≥ 120 days and ≤ 366 days from Dose 3	X	X	X ^e					
Unsolicited AEs		X	X	X	X				
SAEs, Protocol specified AESIs, MAAEs, and NOCMCs		X	X	X	X	X	X	X	X
Nasal or NP swab for PCR & Sequencing								X ^f	
Immunoassays									
Serum- Humoral Assays			32		32	32	32		32
PBMC Cellular Assays & plasma			64		64			64	64
Daily Volume (mL)			96		96	32	32	96	96
Cumulative Volume (mL)			800		896	928	960	1056	

^a Second Booster dose will be the 50 mcg dose of Moderna mRNA-1273.222. It will be administered on study day 1C which is ≥ 120 and ≤ 270 days after the third vaccine dose. If no booster administered; safety visits will continue as per Table 6.

^b Telephone visit

^c Vital signs before and after vaccination. Otherwise, only as clinically indicated.

^d For women of childbearing potential, a negative urine pregnancy test on Day 1C (Second boost) will be performed with negative results confirmed prior to each dosing

^e Review 7-day Memory Aid data for second booster dose.

^f Collect nasal or NP swabs (x 2) for PCR. Sequencing will be performed on all Illness visit-confirmed SARS-CoV-2 specimens.

Table 6: SOA for Cohort 2 Volunteers who do not proceed to first Study Booster

Study Day	181 ^a	366 ^a	Early Term Visit
Visit Number	6	12	
Window (+/-)	28	28	
Informed Consent			
Eligibility Criteria			
Medical History			
Vaccination			
Concomitant Meds			
Interim History	X	X	X
Physical Exam - Targeted	X	X	X
Vital Signs			
Height/Weight (BMI)			
Urine β -HCG			
Memory Aid, Solicited AEs			
Unsolicited AEs			
SAEs, Protocol specified AESIs, MAAEs, and NOCMCs	X	X	X

^aFrom the date of the last study vaccine

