infection. They will be assigned to receive COVID-19 vaccine under EUA dosing (as programmatically outlined in Table 9. Additional pools of subjects can be included if needed as additional COVID-19 vaccines are awarded EUA. These pools of participants were to be assigned a novel homologous or heterologous variant boost or heterologous platform boost at a minimum of 12 weeks following receipt of EUA dosing and followed through 12 months after the last vaccination. As booster vaccines have been approved for individuals at an interval of 6 months from the primary series, under EUA, all Cohort 2 volunteers will be offered a booster of mRNA-1273 at the approved 50 mcg dose at Day 181 (+/- 30 days following dose 2 of their primary series. A telephone visit will occur one week after each primary EUA vaccination and one week after the booster dose. In person follow-up visits will occur on 14 days following completion of EUA vaccinations and on days 14, and 28 days after the booster dose, as well as 3, 6, and 12 months post the booster vaccination. A fourth dose of COVID-19 vaccine will be administered to participants using the Moderna mRNA-1273.222 bivalent vaccine at an interval of 4 to 12 months after the third dose (1st booster). In addition to the other immunologic assays planned for earlier parts of the study (including innate, cellular and humoral responses), samples also will be collected to measure mucosal immune responses before the booster dose and on days 14 and 28, and at 3 months and 6 months after the fourth dose (2nd booster). Due to the surge of the Omicron variant and breakthrough infections, volunteers who contract symptomatic or asymptomatic COVID-19 between completion of their EUA primary series and the scheduled booster dose will be allowed to continue in the study. The interval between the COVID-19 infection and booster dosing should be a minimum of 28 days.

Table 9: Cohort 2 Treatment Arms

Group	Sample Size	First Vaccination	Second Vaccination		Booster Vaccination 1		Booster Vaccination 2	
		Product and Dose	Interval	Product and Dose	Interval	Product and Dose	Interval	Product and Dose
1	250	100 mcg mRNA-1273	28 days	100 mcg mRNA-1273	~6 months	50 mcg mRNA-1273	4-12 months	50 mcg mRNA-1273.222

For both Cohorts 1 and 2, reactogenicity will be assessed at the above-mentioned visits and blood will be drawn for immunogenicity assays at the in-person follow-up visits.

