Study Day	-28 to -1	1	8	29	36	43	Delayed Boost to occur \wedge Day 181 (window +/- 30 days) from Dose	1B	8B	15B	29B	91B	181B	366B	Early Termination Visit	Total Volume of Blood Drawn (mL)
Visit Window (\pm number of days)		0	1	2	3	3		0	1	2	2	7	14	28		
Study Visit	Screening (optional) 00	01	02	3	04 ³	05 ³		06 ³	07 ³	08 ⁴	09 ⁴	10 ⁴	11 ⁴	12 ⁴		
Vaccination		X		X				X								
Serum for Serological Immunogenicity Assays ¹		16		16		16		16		16	16	16	16	16	16 ²	144
PBMCs (and Plasma) for Cellular Immunology Assays		64		64		64		64		64	64	64	64	64	64 ²	512
Serum for Secondary Research		16		16		16		16		16	16	16	16	16	16 ²	144
Per Visit Blood Volume Total (mL)		96		96		96		96		96	32	96	96	96	96 ²	800
Cumulative Blood Volume (mL) (prior 56 days)		96	96	192	192	288	96	96	192	224	96	96	96			
Running Blood Volume Total (mL)		96	96	192	192	288	384	384	480	512	608	704	800			

¹ Inability (e.g., failure of venipuncture) to collect all baseline samples on Day 1 will not exclude the subject from further participation in this study as long as a minimum of baseline blood volume is collected. Refer to the Blood Collection Summary Table in the MOP for the minimum number of expected aliquots for this blood draw volume and minimum aliquots required to completed testing under the protocol

² These blood volumes are not included in the blood volume totals.

³ Visits 05-07 windows should be based off the actual Visit 03 date.

⁴ Visits 08-12 windows should be based off the actual Visit 06 date.

Table 12: Venipuncture Volumes for Cohort 2: (Fourth Vaccination)

Study Day		1C	8C	15C	29C	91C	181C	Illness/ Unscheduled Visit	Early Termination Visit
Visit Number	Boost to occur \geq 120 days \leq 366 days from Dose 3	13	14	15	16	17	18		
Window (+/-)		0 ¹	1 ²	2 ²	2 ²	7 ²	14 ²		
Immunoassays									
Serum- Humoral Assays		32		32	32	32	32		32 ³
PBMC Cellular Assays & plasma		64		64			64		64 ³
Daily Volume (mL)		96		96	32	32	96		96 ³
Cumulative Volume (mL)		96		192	224	256	352		
Running Blood Volume Total (mL) ⁴		800		896	928	960	1056		

¹ Visits 13 windows should be based off the actual Visit 06 date.

² Visits 14-18 windows should be based off the actual Visit 13 date.

³ These blood volumes are not included in the blood volume totals.

⁴ Running blood volume continues after visit 11 for those receiving a 2nd booster in cohort 2 (will occur prior to originally planned visit 12). For subjects who are boosted after visit 10, the running blood volume will be 96 mL less.

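### For Cohort 2 participants given the first booster but not the second, Table 5 footnote a points to a schedule without blood, contradicting the 96 mL visit 12 draw in Table 4

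*Protocol*

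**What the plan says.** **Planned follow-up after the first booster.** Protocol section 4.1 schedules Cohort 2 in-person visits on days 14 and 28 "as well as 3, 6, and 12 months post the booster vaccination", and says blood for immunogenicity is drawn at the in-person visits of both cohorts. Table 4 carries this through to visit 12 (366B, ± 28 days), with 32 mL serum and 64 mL for PBMC and plasma. Table 7 reads the humoral co-primary endpoint at all timepoints. Section 9.4.3 reports GMT, GMFR and seroconversion for every group at every timepoint.

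**Participants who receive the second booster.** Table 12 footnote 4 says of the second booster that it "will occur prior to originally planned visit 12". These participants move to visits 13–18 in Table 5.

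**Participants who do not.** Table 5 footnote a, which describes the second booster, says: "If no booster administered; safety visits will continue as per Table 6". The heading it points to is "Table 6: SOA for Cohort 2 Volunteers who do not proceed to first Study Booster". Table 6 lists interim history, targeted examination and safety events at Days 181 and 366, counted from the last study vaccine. It has no immunoassay or blood-volume rows.

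**Second-booster window.** The Table 5 body says "Boost to occur ≥ 120 days and ≤ 366 days from Dose 3". Table 12 agrees, and section 4.1 gives 4 to 12 months. Footnote a itself sets the upper limit at 270 days.

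**The concern.** Footnote a is the only explicit instruction for someone who has had three doses and does not get the fourth, and it leads to a table written for other people. The same sentence stands in Table 4 footnote d, where the booster in question is the first and the cross-reference fits. It was probably carried over.

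The consequence is practical. One site can draw blood at visit 12 under Table 4 while another draws none under Table 6, and both can say they followed the schedule. A sample not drawn cannot be recovered. Since second-boosted participants have left by then, the people affected are the main source of data on how the first-booster response persists at 12 months without a fourth dose.

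**Working it through.** **1. Do second-boosted participants supply visit 12?** The running blood volumes answer this.

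Inputs: the per-visit totals in Table 11 are 96 (Day 1), 96 (Day 29), 96 (Day 43), 96 (1B), 96 (15B), 32 (29B), 96 (91B), 96 (181B) and 96 (366B). They sum to the stated 800 mL. Table 12 gives 96, 96, 32, 32 and 96 for 1C, 15C, 29C, 91C and 181C.

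- Through visit 11 (181B): 7 × 96 + 32 = 704 mL.
- Skipping visit 12: 704 + 96 = 800 at 1C, then 896, 928, 960, 1056. This is Table 12's running total exactly.
- Including visit 12: 800 + 96 = 896 at 1C, then 992, 1024, 1056, 1152. This does not match.
- Boosting after visit 10: 608 + 96 = 704 at 1C, ending at 960, which is 96 below 1056. This agrees with footnote 4: "For subjects who are boosted after visit 10, the running blood volume will be 96 mL less".

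So the protocol's own arithmetic leaves visit 12 out for second-boosted participants.

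**2. Visit 12 for a participant with three doses.**

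| | Table 4 | Table 6 |
|---|---|---|
| Visit number | 12 | 12 |
| Time origin | first booster (dose 3) | last study vaccine, here dose 3 |
| Day and window | 366 ± 28 (338–394) | 366 ± 28 (338–394) |
| Blood | 32 + 64 = 96 mL | none listed |

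Visit number, day and window coincide; only the draw differs. Table 6 also labels Day 181 as visit 6, a number these participants have already used for Day 1B. That is further evidence that the table was not built for them.

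**3. How many visit 12 samples are at issue?** About 250 are planned. Second-booster uptake is not stated, so 50–90% is assumed. The 10% attrition figure in section 9.2.1 is given for Cohort 1 group sizes and is applied here as an assumption.

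If Table 6 replaces Table 4: 0. If Table 4 stays in force: 250 × (1 − attrition) × (1 − uptake).

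| Uptake | No attrition | 10% attrition |
|---|---|---|
| 50% | 125 | 112.5 |
| 70% | 75 | 67.5 |
| 90% | 25 | 22.5 |

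For precision, the 95% limits of the GMT are GMT ×/÷ exp(t₀.₉₇₅,ₙ₋₁ × SD/√n). With the larger SD in Table 14 (1.0 on the log_e scale), n = 125 gives a factor of 1.19. For n = 25 and n = 22, Table 14 itself shows upper limits of 151.1 and 155.8 around a GMT of 100, factors of 1.51 and 1.56.

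**4. Could Day 1C draws stand in?** The Day 1C draw is taken to be pre-dose.

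- 366-day limit: Days 338–366 fall in the 366B window, which is 29 of the 247 days from 120 to 366 (11.7%). If second boosters were spread evenly over those days (an assumption), the count is 250 × (1 − attrition) × uptake × 29/247, or about 13 (50% uptake, 10% attrition) to 26 (90% uptake, no attrition).
- 270-day limit: none, because 270 is below 338.

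**The case against.** The strongest reply is that footnote a speaks only of safety visits and nowhere cancels a blood draw. Table 4's heading says it applies before the second booster, which still describes someone who never gets it. Section 7.1.4 asks that remaining procedures be completed after study intervention is discontinued. Table 6's title excludes these participants. On that reading visit 12 keeps its 96 mL. The reading is reasonable, and it rules out asserting that the draws are stopped. It does not remove the contradiction: section 7.1.4 defers to the schedule of activities, and the schedule's one explicit pointer for this group is Table 6.

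Four stronger conclusions are tempting and are not supported:

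- *Almost nobody will give a 12-month sample.* This follows only if Table 6 displaces Table 4, which the documents do not say.
- *The 6-month (181B) sample is lost as well.* 181B falls at Days 167–195, before either window closes. Losing it would need an early decision not to boost and an immediate move to Table 6, and no text describes such a move.
- *Second-boosted participants skipping visit 12 is a planning error.* The synopsis says the pool will be followed for the response to a fourth dose, and Table 12 states the consequence openly. It is a deliberate trade-off.
- *Participants without the second booster are the only source of persistence data.* Second-boosted participants still give 91B, usually 181B, and a 1C draw that may fall late enough to count.

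It is also true that no hypothesis attaches to 366B (section 9.1) and that section 9.2.2 estimates GMTs only where samples are collected. A thin timepoint would breach no stated test; the loss would be descriptive.

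**Conclusion.** The contradiction is established from the text: for participants with the first booster but not the second, visit 12 carries 96 mL in Table 4 and no blood in Table 6. What is at risk is a planned timepoint of a co-primary endpoint: 0 visit 12 samples on one reading, about 22 to 125 on the other. The upper range rests on assumed uptake of 50–90% and attrition of 0–10%, and actual uptake could fall outside it. Late 1C draws might add about 13 to 26 under the 366-day limit if timing were even, and add none under footnote a's 270-day limit, so the conflict between those limits also bears on the size.

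Even on the favourable reading, 366B would describe only participants who had not received the second booster by then. They are self-selected and may differ from the rest of the cohort. The supplied SAP covers Groups 4E–6E; its section 2.1 assigns Cohort 2 to a separate report and SAP, so it does not settle the matter. The point should be corrected, though it does not undermine the trial's main results.

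**What to change.** - Correct Table 5 footnote a so that participants who received the first booster but not the second stay on the remaining Table 4 visits, with the blood draws listed there. Keep Table 6 for the population in its title.
- Reconcile the 270-day and 366-day upper limits for the second booster across Table 5 footnote a, the Table 5 body, Table 12 and section 4.1. Which limit applies is for the sponsor to settle.
- In the Cohort 2 SAP, describe any 366B summary as coming from the self-selected subset not second-boosted by that time, and report its n. Whether an in-window 1C draw may be summarised as 366B is an analyst's choice for that document, which may already address it.

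The cost is one footnote, one reconciled window and a sentence in the Cohort 2 SAP. Tables 4 and 11 already budget the draws within the 800 mL total, so no procedure is added.
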